**Inclusion criteria:**

1. Be willing and able to understand and sign the informed consent form (ICF)
2. Men or non-pregnant women age 22 or older
3. Clear intraocular media other than cataract
4. Diagnosis of dry eye disease (OSDI score  $\geq 13$ )
5. Non-invasive Tear break up time  $\leq 10$  seconds in at least one eye
6. Willing and able to comply with all study related visits and procedures
7. In the opinion of the investigator, patients who are appropriate for advanced technology lens implants

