## Clinical Study Protocol Synopsis

**Title:** A Prospective, Single-Arm Study Evaluating Crosslinked Hyaluronate Canalicular Gel for the Treatment of Dry Eye Disease in Patients Undergoing Refractive Cataract Surgery

**Principal Investigator:** [name], OD / [name]

**Sponsor Location:** Vance Thompson Vision  
[name]  
[name]

**Study Name:** Crosslinked Hyaluronate Canalicular Gel: A Benefit Study

**Objective:** To determine patient reported outcomes of hyaluronate crosslinked canalicular gel placed in patients undergoing refractive cataract surgery

**Background:** Dry eye disease (DED) is a prevalent condition among patients presenting for cataract surgery, with nearly 50% exhibiting signs of DED, even if asymptomatic. As a result, DED is often undiagnosed and underreported in patients undergoing cataract surgery. This pre-existing condition can be exacerbated by the surgical procedure itself, leading to increased ocular surface irritation, fluctuating vision, and overall discomfort after surgery. Consequently, despite achieving an improvement in vision from the cataract removal, patients may report dissatisfaction due to these persistent DED symptoms, highlighting a critical gap in aligning surgical success with patient-reported outcomes.

The cataract surgery process, involving corneal incisions and abundant use of perioperative medications, can disrupt tear film stability and worsen DED. Therefore, perioperative identification and management of DED is essential to optimize the visual and refractive outcome of the surgery. Addressing ocular surface health prior to surgery contributes to improved accuracy of biometric measurements, which are critical for intraocular lens (IOL) power calculations and achieving desired refractive targets. Proactive management helps stabilize and prepare the ocular surface, potentially reducing postoperative complications and ensuring that patient expectations are more closely met.

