Fortunately, the dry eye treatment landscape continues to evolve which enables more individualized care for patients. Recently, a cross-linked hyaluronic acid canalicular gel (Lacrifill®) was introduced, which represents a novel, alternative solution for lacrimal occlusion. This treatment works by occluding the tear drainage system, thereby increasing the retention of natural tears, improving tear film stability, and reducing ocular surface irritation. Proactive use of the canalicular gel could lead to more reliable pre-operative measurements, better visual outcomes, and increased post-operative comfort, which is particularly important for

patients receiving advanced technology IOLs. Improvements in both signs and symptoms of DED have been reported using lacrimal occlusion, suggesting it could play a valuable role in optimizing the cataract surgery experience.

**Study Design:** Prospective, single-site, single-arm study enrolling 60 patients who have elected advanced IOL implantation at the time of cataract surgery and have a diagnosis of dry eye disease. The study will consist of 5 study visits, over a 3-5 month time period. Patients will receive bilateral lacrimal occlusion of crosslinked hyaluronate canalicular gel pre-operatively

The primary endpoint will be the change from baseline to 3- month visit in non-invasive tear break up time (NITBUT) in primary eyes as measured by a non-invasive, automated ocular surface analyzer. Additional endpoints measured will be the change from baseline in the visual analog score and OSDI. The effect of pre-operative lacrimal occlusion on accuracy of preoperative biometry/keratometry measurements will be evaluated as well as residual refractive error at 30 and 90 days post-operative.

**Subject Population:** 60 subjects, who have elected bilateral refractive cataract surgery will be enrolled.

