## Materials and Methods

- Informed consent will be obtained prior to collection of any study specific data.
- Each subjects' demographics, medical and ocular history will be reviewed.
- Inclusion and exclusion criteria will be reviewed for each subject.
- Subjects will be asked to report satisfaction using the visual Analog Score (VAS) and dry eye symptoms using the Ocular Surface Disease Index (OSDI)
- Subjects' monocular and binocular uncorrected distance visual acuity (UDVA) will be obtained on an ETDRS chart at a distance of 4 meters
- A manifest refraction will be performed on each subject.
- Monocular and binocular best corrected distance visual acuity (BCDVA) will be obtained on an ETDRS chart at a distance of 20 feet in photopic lighting conditions.
- Biometry measurements will be obtained.
- Objective tear meniscus height will be measured.
- Objective non-invasive tear break up time will be measured.
- The subjects' eyes will be thoroughly examined at the slit lamp.
- Bilateral canalicular occlusion with cross-linked hyaluronate will be performed prior to cataract surgery
- Patients will undergo standard of care cataract post-operative visit testing and procedures

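### Change in OSDI, the only dry-eye symptom measure, spans cataract removal with no control arm, so it mixes any gel effect with the vision gain from surgery

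*Protocol*

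**What the plan says.** The Synopsis gives the objective as "To determine patient reported outcomes of hyaluronate crosslinked canalicular gel placed in patients undergoing refractive cataract surgery". Materials and Methods assigns the visual analog score to satisfaction and uses the OSDI for the symptoms: "dry eye symptoms using the Ocular Surface Disease Index (OSDI"). The OSDI is therefore the only dry-eye symptom scale in the study.

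It has two uses:

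- **Entry.** Inclusion criterion 4 is "Diagnosis of dry eye disease (OSDI score" of 13 or more). Criterion 5 separately requires "Non-invasive Tear break up time" of 10 seconds or less in at least one eye.
- **Endpoint.** Study Design states: "Additional endpoints measured will be the change from baseline in the visual analog score and OSDI". The primary endpoint is change in NITBUT, not OSDI.

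The design is a "Prospective, single-site, single-arm study enrolling 60 patients". All patients have a cataract at entry (criterion 3: "Clear intraocular media other than cataract"). OSDI is collected at Visit 0, before the gel and before surgery, and then at Visits 3, 4 and 5, about 7, 30 and 90 days after surgery. The Visit 1A/B list includes the visual analog score but no OSDI.

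**The concern.** Between the baseline OSDI and every later one, two things happen to each patient: the gel is placed and the cataract is removed. The protocol's Background treats vision and dry-eye symptoms as separate matters, noting that "despite achieving an improvement in vision from the cataract removal, patients may report dissatisfaction due to these persistent DED symptoms". A questionnaire score that includes questions about vision or visual tasks puts the two back together. Part of the baseline score would then reflect cataract blur, and that part could fall after surgery even if the gel did nothing.

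At stake is what the trial can say about symptoms. The objective is patient-reported, and the OSDI is the measure that speaks to dry-eye symptoms. A fall in the score at 90 days would naturally be read as dry-eye relief from the gel, and the design has no comparison that could correct that reading.

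**Working it through.** **Inputs from the protocol.** OSDI cut-off 13 (Inclusion criteria, 4); NITBUT at most 10 s in at least one eye (Inclusion criteria, 5); OSDI at Visits 0, 3, 4 and 5 only; single arm, 60 patients.

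**Assumed inputs.** The protocol gives neither the OSDI items nor the scoring rule. Assumed here: 12 items graded 0 to 4; score = sum of grades x 25 / items answered; all 12 answered; about 6 items concerning vision or visual tasks, varied from 4 to 7.

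The plan has no OSDI effect size or power figure to reproduce. Its sample size concerns NITBUT and plays no part here.

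**Step 1. Effect of vision items alone on the change score.** With k vision items each improving by one grade and no other item changing, the total falls by k x 25/12. The most that k vision items can contribute is k x 4 x 25/12.

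| Vision items k | Fall in total for one grade on each | Maximum score from vision items alone |
|---|---|---|
| 4 | 8.3 | 33.3 |
| 5 | 10.4 | 41.7 |
| 6 | 12.5 | 50.0 |
| 7 | 14.6 | 58.3 |

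The fall is close to the size of the entry cut-off itself.

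**Step 2. Can vision items alone meet criterion 4?** The raw sum needed is 13 x 12/25 = 6.24, so 7 points. A raw sum of 6 scores 6 x 25/12 = 12.5 and fails; 7 scores 7 x 25/12 = 14.6 and passes. The mean grade needed on k vision items is 7/k: 1.75 for k = 4, 1.17 for k = 6 and 1.0 for k = 7. Criterion 4 can thus be met by vision complaints alone anywhere in the range.

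**Step 3. Opposing effects.** The Background says surgery can also aggravate dry eye. With k = 6, if the six vision items improve by one grade and the other six worsen by one grade, the total changes by (-6 + 6) x 25/12 = 0, although each half has moved by 12.5 points. An unchanged total is therefore no easier to interpret than a fall.

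**Step 4. Is there any OSDI that separates gel from surgery?** None is scheduled after gel placement and before surgery, and there is no untreated group. The schedule supplies no internal comparison.

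**The case against.** **The premise comes from outside the protocol.** Item content, item count and scoring are not in the document. This stands, which is why they are labelled as assumptions and given with a range. The size depends on them. The schedule and the missing control arm do not.

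**Questionnaire scoring belongs in the analysis plan.** The endpoint sentence says only change in OSDI; it neither specifies the total nor excludes sub-scores. This stands in part: if an analysis plan already separates the items, the reporting request is met. But the protocol itself fixes what the OSDI is taken to measure, when it is collected and that its change is an endpoint, and those choices create the confounding.

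**Enrolment does not depend on the OSDI alone.** A reader might infer that cataract alone can bring a patient into the study. The protocol does not support that: criterion 5 also demands a short NITBUT in at least one eye. Vision complaints could satisfy criterion 4, but not full eligibility.

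**An improvement is not assured.** A reader might also infer that any OSDI gain will be cataract removal and nothing else. That does not follow. The 12.5 points are a worked scenario, not an estimate, and surgery may push discomfort the other way.

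**Vision items are not foreign to dry eye.** The Background lists unstable vision among the consequences of aggravated dry eye, and the protocol expects the gel may help visual outcomes. This stands. It argues against discarding the vision items or replacing the total, but not against showing the two parts side by side.

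**There is another patient-reported measure.** The visual analog score is also collected on the operative day, but the protocol assigns it to satisfaction, so it does not fill the gap for symptoms.

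**Conclusion.** The point holds as a limit on interpretation of an additional endpoint. Change in OSDI from Visit 0 to Visits 3, 4 and 5 includes whatever cataract surgery does to the score and, with no control arm, cannot be credited to the gel alone. On the stated assumptions, one grade of improvement on the vision items alone is worth about 12.5 points (8.3 to 14.6 for 4 to 7 items), against an entry cut-off of 13. The direction of the net bias is not established.

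The entry criterion is a lesser matter: vision complaints can meet criterion 4 throughout the assumed range, with NITBUT as the separate objective check. The primary NITBUT endpoint is untouched by this point. It is still worth acting on, because the stated objective is patient-reported and this is the only scale aimed at dry-eye symptoms.

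**What to change.** 1. Keep the OSDI total as an endpoint. Pre-specify that two sub-scores are reported beside it at each visit: the non-vision items (discomfort and environmental triggers) and the vision items, each rescaled 0 to 100 by the same rule. List which items fall in each group.
2. Base any statement about change in dry-eye symptoms on the non-vision items.
3. State in the protocol, and in any report, that change in the total includes the effect of cataract removal and, with no control arm, cannot be attributed to the gel alone.

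The entry criteria need no change.

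**Cost.** The questionnaires are already being collected, so this is item-level data entry and scoring, with no extra visit or patient burden. The non-vision sub-score is somewhat noisier: with 6 items, one grade on one item moves it by 25/6 = 4.2 points, against 25/12 = 2.1 on the total (25/8 = 3.1 to 25/5 = 5.0 across the assumed range).

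The split does not supply a control. Non-vision items remain exposed to other effects of surgery, and light sensitivity may itself respond to cataract removal. Adding an OSDI before surgery could inform on an early gel effect but would leave the 7-, 30- and 90-day totals as mixed as they are now.

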**Exclusion criteria:**

1. History of punctal cauter
2. Lacrimal anatomy (e.g., nasolacrimal duct obstruction) that per investigator suggests that the patient would not be a good candidate for lacrimal occlusion or patients for whom lacrimal occlusion would increase risk

**Procedures**

Subjects will be recruited from the site's current patient population who have been scheduled for refractive cataract surgery and have a concomitant diagnosis of dry eye disease. Enrollment and informed consent will be administered by study coordinators. Data will be collected by investigators and study coordinators as follows.

**Visit 0 (7 to 45 days prior to surgery):**

- Informed consent will be obtained prior to collection of any study-specific data.
- Potential subjects' demographics, medical and ocular history, and concomitant medications will be reviewed.
- Inclusion and exclusion criteria will be reviewed for each subject.
- Ocular Surface Disease Index (OSDI) will be obtained
- Visual Analog Score will be obtained

- Pre-operative biometry measurements will be obtained
- Non-invasive tear break up time (NITBUT) will be obtained
- Automated tear meniscus (TMH) will be obtained
- Best-corrected distance visual acuity (BCDVA) will be obtained using the ETDRS
- Slit Lamp Exam
- NaFl staining will be measured (NEI grading scale)
- If both eyes qualify for the study, the primary eye will be the eye with the smaller NITBUT. If the NITBUT is the same in both eyes, the primary eye will be the right eye.
- Lacrimal occlusion of the inferior canaliculi of both eyes will be performed

**Visit 1A/B (operative day[s]):**

- Repeated biometry measurements obtained on each eye
- VAS
- Patients may undergo sequential bilateral surgery per site standard of care
- Adverse events will be collected

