**Visit 2 (1-2 days post-op):**

- UCDVA as measured by ETDRS
- Slit lamp exam
- Corneal fluorescein staining
- Intraocular pressure measured by standard of care
- Adverse events will be collected

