**Visit 3 (7 days post cataract surgery +/- 2 days)**

- OSDI
- VAS
- NITBUT
- TMH
- Manifest refraction
- UCDVA/BCDVA measured by ETDRS
- Slit lamp exam
- Corneal fluorescein staining
- Intraocular pressure measured by standard of care
- Adverse events will be collected

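### Must the protocol say which eye's surgery starts the clock for Visits 2 to 5 when the eyes are operated on different days?

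*Protocol*

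**What the plan says.** Study Design in the protocol synopsis enrols patients for surgery on both eyes and states: "The study will consist of 5 study visits, over a 3-5 month time period". The schedule then numbers its visits from 0 to 5.

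- Visit 0 is headed "Visit 0 (7 to 45 days prior to surgery", with no eye named. The gel is placed in both eyes at this visit. The primary eye is chosen here too: "If both eyes qualify for the study, the primary eye will be the eye with the smaller NITBUT".
- The operative visit is headed "Visit 1A/B (operative day[s" and adds: "Patients may undergo sequential bilateral surgery per site standard of care". No interval between the eyes is given.
- The next headings are "Visit 2 (1-2 days post-op" and "Visit 3 (7 days post cataract surgery +/- 2 days". Visits 4 and 5 follow the same pattern at 30 ± 7 and 90 ± 14 days. None of the four is split into A and B.

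The primary endpoint is the change in NITBUT in the primary eye from baseline to 3 months. For the symptom scores, Study Design says: "Additional endpoints measured will be the change from baseline in the visual analog score and OSDI". It attaches no day to them. Residual refractive error is tied to days 30 and 90. The Data Analysis section adds secondary analyses of fellow eyes and of all eyes.

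**The concern.** With two operative days there are two possible starting dates for each later window, and the protocol does not choose between them. Once the operations are further apart than a window is wide, no single visit is on time for both eyes.

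Three things seem to be at stake:

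- OSDI and VAS belong to the patient, not to an eye, and patient-reported outcomes are the stated objective. A Visit 3 score counted from the first operation may be taken with one eye still unoperated. Counted from the second operation, both eyes are done. The same visit label would then cover two different states.
- The primary eye is picked by NITBUT and not by order of surgery, so it may be the second eye. On a first-surgery clock its 3-month reading would come early relative to its own operation.
- The stated visit count of five does not match the six numbered visits, which suggests the schedule was not thought through for staged surgery.

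**Working it through.** **Inputs.** Windows in days after surgery, from the visit headings: Visit 2, 1–2; Visit 3, 5–9; Visit 4, 23–37; Visit 5, 76–104. Visit 0 is 7–45 days before surgery. The gap *d* between the operations is not in the protocol and is assumed below.

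**Visit count.** Visits 0 to 5 make 6. Leaving out Visit 0 as a screening visit, and taking 1A/B as one numbered visit, gives 5, the stated figure. Counting each operative day gives 1 + 2 + 4 = 7. Repeating Visits 2–5 for each eye gives 1 + 2 + 8 = 11, an upper limit. So one reading does reproduce the 5. It is awkward, because the gel is placed at Visit 0, but it exists.

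**Study span.** With one operative day, Visit 0 to Visit 5 takes 7 + 76 = 83 to 45 + 104 = 149 days. At 30.4 days a month that is 2.7 to 4.9 months, in line with the stated 3–5 months.

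**When one visit serves both eyes.** This requires *d* to be no more than the window's last day minus its first: 2 − 1 = 1, 9 − 5 = 4, 37 − 23 = 14 and 104 − 76 = 28 days for Visits 2 to 5. If the Visit 0 window binds both eyes, *d* can reach 45 − 7 = 38 days.

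**Visit 5 on a first-surgery clock.** It falls on second-eye day 76 − *d* to 104 − *d*:

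| Gap *d* (assumed) | Second-eye day at Visit 5 | Days of 29 outside that eye's window |
|---|---|---|
| 0 | 76–104 | 0 |
| 7 | 69–97 | 7 |
| 14 | 62–90 | 14 |
| 28 | 48–76 | 28 |
| 38 | 38–66 | 29 |

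Even in the last row the second eye was operated on at least 38 days earlier. If each eye is timed from its own operation, the last column is 0 throughout.

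**Time since the gel.** Both eyes receive it at Visit 0. If Visits 0 and 5 are both timed from the first operation, Visit 5 comes 83–149 days after the gel in both eyes, whatever *d* is. The protocol already accepts that spread.

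**Visits 3 and 4 on a first-surgery clock.** Visit 3 is second-eye day 5 − *d* to 9 − *d*. From *d* = 5 no day is in that eye's window. From *d* = 10 every day precedes its operation (−5 to −1). Visit 4 is second-eye day 23 − *d* to 37 − *d*. No day is in window from *d* = 15, and some days precede the second operation from *d* = 24.

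**What separate clocks would cost.** Suppose eye-level readings ran from each eye's own operation and OSDI and VAS from the second. With *d* = 7 and the primary eye first, its Visit 3 NITBUT is due on days 5–9 after the first operation. The scores are due on days 7 + 5 = 12 to 7 + 9 = 16. That is two Visit 3 attendances even if only the primary eye is measured.

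**The case for a change.** The strongest case for a change is that timing each eye from its own operation cannot settle OSDI and VAS, which have no eye. Visit timing governs data collection, and no later analysis rule can recover a score taken before the second operation. The protocol itself foresees two operative days, so this is not a remote possibility. In staged patients the all-eyes analysis always contains a second-operated eye, and the primary eye may be that eye.

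Much of this is true as description. The anchor is unstated, and a Visit 3 symptom score in a staged patient can be ambiguous. Three points limit what follows.

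- The ambiguity is worst at day 7, where Study Design names no endpoint timepoint. At Visit 5, when the 3-month primary analysis is due, both eyes have been operated on at every gap considered.
- For eye-level measures, a window described as days after cataract surgery is naturally read as days after surgery on that eye. A refractive error 30 days after surgery has no other sensible meaning. Each operative day is itself a visit, so its date should be on record. Assigning readings to windows can then be left to the analysis plan, which is not at hand.
- The fellow eye is not always the second eye. If the primary eye goes second, the fellow eye went first.

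Visit 2 carries none of NITBUT, OSDI, VAS or refraction. How its checks relate to two operative days is for the sponsor to reconcile, and it does not bear on the analysis.

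**Conclusion.** No change to the plan follows. The missing anchor is a gap that the site and the analysts would fill sensibly, and the count of five visits is a numbering convention or a clerical slip.

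On the natural reading, with each eye timed from its own operation, primary-eye NITBUT at Visit 5 is unaffected at any gap. What remains is possible ambiguity in OSDI and VAS in staged patients. At Visit 3 it is complete on a first-surgery clock from a gap of 10 days. At Visit 4 it begins at 24 days. By Visit 5 both eyes are done.

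This rests on two assumptions: that the site reads the windows eye by eye, and that gaps do not exceed the 38 days implied by the Visit 0 window. With both eyes operated on the same day there is no effect at all. The protocol gives neither the gap nor the share of staged patients, so no shift in seconds of NITBUT or in OSDI points can be derived, and none has been shown.

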**Visit 2 (1-2 days post-op):**

- UCDVA as measured by ETDRS
- Slit lamp exam
- Corneal fluorescein staining
- Intraocular pressure measured by standard of care
- Adverse events will be collected

**Visit 3 (7 days post cataract surgery +/- 2 days)**

- OSDI
- VAS
- NITBUT
- TMH
- Manifest refraction
- UCDVA/BCDVA measured by ETDRS
- Slit lamp exam
- Corneal fluorescein staining
- Intraocular pressure measured by standard of care
- Adverse events will be collected

**Visit 4 (30 days post cataract surgery +/- 7 days)**

- OSDI
- VAS
- NITBUT
- TMH
- Manifest refraction
- UCDVA/BCDVA measured by ETDRS
- Slit lamp exam
- Corneal fluorescein staining
- Intraocular pressure measured by standard of care
- Dilated fundus exam
- Adverse events will be collected

